4.2 Exclusion Criteria

Women who meet any of the following criteria will be excluded from this study:

- 4.2.1 Evidence of confirmed or probable active TB disease per WHO symptom screen and confirmation by Gene Xpert, shielded chest x-ray, or sputum sample
- 4.2.2 Participant report of personal history of INH- or rifampin-resistant, multi-drug resistant (MDR), or extensively drug-resistant (XDR) TB
- 4.2.3 Participant report of personal history of active TB in the past 2 years

- 4.2.4 Participant report of previous treatment for LTBI
- 4.2.5 Household contact (as defined above) with known active MDR or XDR TB disease
- 4.2.6 Known major fetal abnormality as detected on ultrasound
- 4.2.7 Known allergy/sensitivity or any hypersensitivity to components of study drugs or their formulation
- 4.2.8 Known history of liver cirrhosis at any time prior to study entry
- 4.2.9 Per participant report and/or medical records, evidence of acute clinical hepatitis, such as a combination of abdominal pain, jaundice, dark urine, and/or light stools within 90 days prior to entry
- 4.2.10 Participant report and/or medical records of peripheral neuropathy Grade 2 or higher within 90 days prior to entry
- 4.2.11 Current use or history of active drug or alcohol use or dependence that, in the opinion of the site investigator, would interfere with adherence to study requirements
- 4.2.12 Participant report and/or clinical evidence of porphyria
- 4.2.13 Any other condition that, in the opinion of the IoR/designee, would preclude informed consent, make study participation unsafe, complicate interpretation of study outcome data, or otherwise interfere with achieving the study objectives, including taking the study medication
- 4.2.14 Planned or current participation in an interventional drug study
- 4.2.15 Current use of any prohibited or precautionary medications (see Section 5.5), including didanosine (DDI) or stavudine (D4T)

4.3 Co-Enrollment Considerations

Participants (i.e., women or infants) cannot be co-enrolled in an interventional drug study. Co-enrollment in other types of studies will be considered on a case-by-case basis. Sites will consult with the IMPAACT 2001 Core Team, [contact], and the other study team for co-enrollment considerations and questions.

4.4 Recruitment, Screening, and Enrollment Process

Study visits and procedures are described in detail in Section 6.

Recruitment: As part of participant outreach and recruitment strategies, study staff may pre-screen potential study participants at either on-site or off-site locations. It is anticipated that many women will be recruited from the antenatal clinic at the site. During these interactions, study staff may explain the study to potential participants and ascertain elements of presumptive eligibility (e.g., age, gestational age), to be confirmed at on-site screening visits. Process information (e.g., number of potential participants contacted, number presumptively eligible) may be recorded and stored at the study site in the absence of written informed consent, provided the information is collected in such a manner that it cannot be linked to potential participant identifiers. At each site, procedures and documentation will comply with local IRB/EC requirements.

Screening: Once referred, study staff will obtain written informed consent. Written informed consent for study participation must be obtained before any study-related procedures are performed. After informed consent is obtained from the woman, a study-specific screening number will be acquired for the mother-infant pair through completion of the IMPAACT Screening Checklist. The checklist is part of the Subject Enrollment System (SES) located on the IMPAACT Data Management Center (DMC) website (at <https://www.fstrf.org>). Participant ID Numbers (PIDs) will be assigned at the site to both the woman and the infant. A PID is retrieved from the site's PID list, which is generated at the DMC and sent to the sites. The screening visit procedures are found in Section 6.

Enrollment: For mother-infant pairs who are found to be eligible for the study, enrollment will occur upon successful entry of required eligibility data into the SES (See Section 6.1). Successful entry into the SES will generate a study identification number (SID) for both the woman and the infant, as well as prescribing information for the study drug regimen. For pairs who are found ineligible or who do not enroll in the study for any reason, a Screening Failure Results case report form will be completed to record the screening outcome. The Entry Visit procedures are found in Section 6.

The DMC will generate monthly screening and enrollment reports. Using these reports, the Protocol Team will monitor accrual closely, relative to the study-specific accrual plan that has been established in collaboration with the study sites. Based on this plan, accrual is projected to be completed within 12 months. Each site must establish and implement SOPs to achieve the projected rates of enrollment specified in the accrual plan. Accrual will be assessed on team calls for each site, with an assessment of any issues surrounding enrollment. Should accrual rates fall below projections, the Protocol Team will work with study sites to take action as needed.

4.5 Participant Retention

Once a woman enrolls in this study, the study site will make every effort to retain her and her infant for the protocol-specified duration of follow-up and thereby minimize potential biases associated with loss to follow-up. Each site must establish and implement SOPs that target retention rates that are sufficient to allow the primary study outcomes to be reliably estimated (a maximum 10% loss to follow-up is assumed in sample size calculations).

The DMC will generate monthly reports of the number and percentage of participants completing follow-up visits throughout the course of the study. Based on these reports, the Protocol Team will track retention closely and work with study sites as needed to take any required action to address below-target rates.

5 STUDY TREATMENT

Study treatment for women consists of 12 once-weekly doses of RPT, INH, and pyridoxine (vitamin B₆). All HIV-1-infected women are required to have been on efavirenz (EFV) + 2 NRTIs (not provided through the study) for at least two weeks prior to enrollment.

Both RPT and INH will be provided through the study.

5.1 Regimens, Administration and Duration of Regimen

5.1.1 Regimens and Administration

The study drug regimen consists of 12 directly observed once-weekly doses of rifapentine (RPT) 900mg (six 150mg tablets), isoniazid (INH) 900mg (three 300mg tablets), and pyridoxine (vitamin B₆) 25mg to 100mg. HIV-1-infected and HIV-1-uninfected pregnant women with latent TB and their infants will be enrolled into two cohorts based upon gestation:

Cohort 1: Pregnant women in the second trimester (≥ 14 to < 28 weeks gestation).

Cohort 2: Pregnant women in the third trimester (≥ 28 to ≤ 34 weeks gestation) and postpartum.

Both cohorts will receive the study drug regimen weekly with food as described in the MOP. The study drug regimen dosing may be adjusted based on an interim analysis (see Section 10 (Clinical Pharmacology Plan)). Doses should be given 7 days part (± 2 days). Women will be provided a meal within 30 minutes prior to each dose. Following this meal, women will swallow whole RPT, whole INH, and whole or crushed pyridoxine tablets under direct observation of site staff (i.e., directly observed therapy, DOT).

Women must receive the appropriate dose of pyridoxine 25mg to 100mg based on the current local, national, or international dosing guidelines. Pyridoxine can be taken as a whole tablet or crushed.

5.1.2 Duration and Adherence

All enrolled women will receive 12 weekly directly observed doses of the study regimen and will be followed until 24 weeks postpartum. Infants will not directly receive the study drug regimen but will be followed on study for the first 24 weeks of life.

Adequate adherence to the study drug regimen is defined as receipt of at least 90% of the prescribed doses. Women are to receive 12 weekly doses within a 16-week window (12 weeks consecutively is optimal). However, they will be considered to have completed the regimen if they receive at least 11 doses (90%) during this 16-week study drug regimen window. Skipped doses should be taken late rather than missed.

If a woman will not complete the therapy in the allotted 16 weeks (e.g., misses four doses in a row), there will be no limit to the number of times she can restart the study drug regimen. That is, if a woman chooses to stop participating or is lost to follow-up per Section 8.3 and then returns to the clinic while still within the gestational age requirements of the protocol, she will be allowed to restart the study drug regimen if she wishes. In this situation, the woman would be enrolled as a new participant into the appropriate cohort based on the gestational age at the time of restarting. The above definition must be met for the regimen to be considered complete.

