8.3 Criteria for Premature Discontinuation of Study Participation

A participant must be withdrawn from study participation if:

- The participant withdraws consent and/or does not wish to continue in the study.
- The site investigator determines further participation would be detrimental to the participant's health or well-being.
- The participant fails to comply with study requirements, so as to cause harm to self or seriously interfere with the validity of the study results.
- The study is cancelled at the discretion of IMPAACT, the Food and Drug Administration (FDA), NIAID, the Office for Human Research Protections (OHRP), the local and/or national IRB or EC, or a country-specific governmental agency.

Note: Lost to follow-up is defined as a participant having missed four or more consecutive study visits without contact with study staff.

See Section 6.10 for procedures to be conducted in the event of premature discontinuation of study participation.

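### Section 5.1.2 uses four consecutive missed doses as its example of a course that cannot be finished, yet such a course usually still can be, so a completable course may be restarted

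*Protocol*

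**What the plan says.** Protocol Section 5.1.2 plans 12 directly observed weekly doses within a 16-week window. Of women who fall short of 12, it says "they will be considered to have completed the regimen if they receive at least 11 doses (90%) during this 16-week study drug regimen window", and it adds "Skipped doses should be taken late rather than missed". Section 5.1.1 sets the spacing at 7 days, plus or minus 2.

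Section 5.1.2 then turns to women who will not finish: "If a woman will not complete the therapy in the allotted 16 weeks (e.g., misses four doses in a row". Four consecutive misses is the only example. The explanatory sentence that follows covers a woman who chooses to stop, or who is lost to follow-up under Section 8.3, and who returns within the gestational age limits: "she will be allowed to restart the study drug regimen if she wishes". In that event, "the woman would be enrolled as a new participant into the appropriate cohort based on the gestational age at the time of restarting". The paragraph ends by saying that the completion definition must still be met.

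Section 8.3 supplies the trigger: "Lost to follow-up is defined as a participant having missed four or more consecutive study visits without contact with study staff". Visits are weekly while a woman is on study drug (Section 6.3).

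**The concern.** The window has four weeks of slack for 12 doses and five for the 11 that count as complete. An example that treats four consecutive misses as the end of the course tells sites it is lost while it can still be finished. The same number is the loss-to-follow-up threshold in Section 8.3, so during weekly dosing a woman can qualify for restart exactly when continuing would still succeed.

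What is at stake is drug exposure. Restart means enrolment as a new participant, and enrolled women are to receive 12 doses. If the first course could have been completed, the doses already taken become additional rifapentine and isoniazid exposure for mother and fetus. Section 1.1 gives the unknown safety of this regimen in pregnancy as the gap the study is meant to address.

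**Working it through.** **Inputs.** 12 doses, a 16-week (112-day) window and completion at 11 doses (5.1.2); spacing of 7 ± 2 days (5.1.1); loss to follow-up at four consecutive missed visits (8.3), with weekly visits on drug (6.3); enrolment at 14 to 34 weeks' gestation (4.1.2).

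**1. The completion threshold reproduces.** 90% of 12 is 10.8, which rounds up to 11. 11/12 = 91.7% and 10/12 = 83.3%.

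**2. The example does not.** At 7-day spacing the window has dose slots on days 0, 7, …, 105: 105/7 + 1 = 16. Counting day 112 gives 17. With k consecutive misses and no others, 16 − k doses fit (17 − k if day 112 counts). A dose n that comes after the gap falls on day 7(n − 1 + k).

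| Consecutive misses k | Doses that fit (16 slots) | Day of 11th | Day of 12th | Complete? | Complete if day 112 counts? |
|---|---|---|---|---|---|
| 4 | 12 | 98 | 105 | yes | yes |
| 5 | 11 | 105 | 112 | yes | yes |
| 6 | 10 | 112 | 119 | no | yes |
| 7 | 9 | 119 | 126 | no | no |

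With four misses, the 11th and 12th doses fall on days 98 and 105 whatever number d of doses (1 to 10) came before the gap.

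**3. When four misses are enough.**
- Two earlier misses: 16 − 4 − 2 = 10 doses. With 17 slots it takes three: 17 − 4 − 3 = 10.
- Spacing of s days throughout apart from one 35-day gap: dose n falls on day 35 + s(n − 2). For s = 8, the 11th is on day 35 + 72 = 107, which is complete (the 12th, on day 115, no longer fits). For s = 9, the 11th is on day 35 + 81 = 116, which is too late.
- 9-day spacing before the gap and 7-day after: the 11th dose is on day 9(d − 1) + 35 + 7(10 − d) = 2d + 96. That is day 110 for d = 7, day 112 for d = 8 and day 116 for d = 10. Four misses therefore prevent completion at d = 9 and 10, and at d = 8 unless day 112 counts.

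**4. Extra doses.** After d doses and four misses at 7-day spacing, continuing takes 12 − d more doses for the full course, or 11 − d to count as complete. Restarting takes 12 more, for a total of 12 + d and an excess of d over the full course. For d = 5, that is 6 more doses to be complete or 7 for all 12, against 12 on restart (17 in total).

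**5. Who can be affected.** She returns d + 4 weeks after entry and must be at 34 weeks or less, so entry must be by about 34 − (d + 4) = 30 − d weeks, ignoring re-screening time.

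| d | Latest entry, four misses (30 − d) | Latest entry, five misses (29 − d) |
|---|---|---|
| 1 | 29 weeks | 28 weeks |
| 2 | 28 weeks | 27 weeks |
| 3 | 27 weeks | 26 weeks |
| 10 | 20 weeks | 19 weeks |

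Cohort 2 enters at 28 weeks or later, so after four misses only d = 1 or 2 qualifies there. The larger values of d arise only in Cohort 1. At d = 8 to 10 she needs just one to three more doses to be complete, so choosing a restart is unlikely.

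**The case against.** The best defence is that the example is not the rule. The sentence opens with a condition, that the woman will not complete in 16 weeks, and the section has just set the 11-dose rule and said that skipped doses are to be taken late. A careful site would keep a woman on her course if 11 doses were still possible. Four is also the limit of the slack for all 12 doses, and step 3 shows it can be enough when dosing runs late within the permitted ±2 days. This stands in part: any fixed count is only a guide. It does not rescue the text. The one example says the condition is met when, on schedule, it is not, and no sentence tells a site to check whether 11 doses remain reachable before offering restart.

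A second defence is that permission to restart comes from the explanatory sentence, so correcting the number alone would change little. That is right, and it is why the fix must cover both sentences.

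Two stronger readings are tempting and are not supported:
- *A returning woman has no route to finish her first course.* In Section 8.3, loss to follow-up is defined in a note and is not among the listed grounds for withdrawal. Section 5.1.2 prefers late doses to missed ones. Continuation remains open to a woman who has not withdrawn; it is simply not stated as the first choice.
- *Exclusion 4.2.4 creates a second harm.* Re-enrolment passes through eligibility again (Section 4.4: "enrollment will occur upon successful entry of required eligibility data into the SES"), and 4.2.4 excludes "Participant report of previous treatment for LTBI" with no exception for doses given in this study. Read literally, it would block the restart and so prevent the extra exposure. If the specific permission in 5.1.2 prevails, 4.2.4 is no obstacle. The two consequences cannot both befall the same woman, so this is a side issue.

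The manual of procedures to which the protocol refers is not available here and may give sites further guidance.

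**Conclusion.** The point holds as a minor correction. Under 7-day spacing and no other missed dose, the example is wrong on either reading of the window's end: four misses leave room for all 12 doses and five for the 11 that complete the regimen. As written, the text permits a woman with a completable course to restart and receive up to 12 further doses.

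The reach is small. It requires a choice to stop, or a run of four or five missed visits without contact; return while still pregnant at 34 weeks or less; passing re-screening; and her own wish to restart. It lies mainly in Cohort 1, and the documents give no expected frequency.

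A reader might infer that completion figures are distorted. They are not, because completion is still judged by the 11-dose rule whatever the example says. No sample size, power or other study estimate depends on it.

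**What to change.** In Section 5.1.2, replace the four-dose example with the condition itself: *can no longer receive at least 11 doses within 16 weeks of her first dose*. If an illustration is wanted, six or more missed doses at weekly spacing is the matching one, with a statement of whether day 112 is inside the window.

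Then add that a woman who returns after stopping or after loss to follow-up and can still meet the condition for completion is offered continuation of her current course. Restart as a new participant is offered only when she cannot.

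Optionally, state that doses taken in this study do not count as previous treatment under exclusion 4.2.4, so that a permitted restart is not blocked at re-screening.

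The cost is two or three sentences of protocol wording, with no new data or visits.

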5.2 Study Drug Formulation

Rifapentine (RPT, Priftin®) will be supplied through the study as tablets for oral administration, each containing 150mg of rifapentine. Store at 25°C (77°F); excursions permitted from 15° – 30°C (59° – 86°F). Protect from light and excessive heat and humidity.

Isoniazid (INH) will be supplied through the study and must be stored in accordance with the manufacturer's instructions.

Pyridoxine (vitamin B₆) will not be supplied through the study and must be stored in accordance with the manufacturer's instructions.

5.3 Product Supply/Acquisition, Distribution and Accountability

5.3.1 Study Product Supply/Acquisition/Distribution

Rifapentine (RPT) will be supplied by Sanofi, and isoniazid (INH) will be supplied by Macleods Pharmaceuticals Limited. Both RPT and INH will be made available through the National Institute of Allergy and Infectious Diseases (NIAID) Clinical Research Products Management Center (CRPMC). The site pharmacist can obtain RPT and INH for this protocol by following the instructions in the manual Pharmacy Guidelines and Instructions for DAIDS Clinical Trials Networks in the section Study Product Management Responsibilities.

Pyridoxine (vitamin B₆) will not be supplied through the study and must be obtained locally by the site. ARVs are not provided by the study and are not considered part of the study drug regimen.

Any study product not provided by the study must comply with the NIAID (DAIDS) policy that outlines the process for authorizing the use of study products not marketed in the US in NIAID (DAIDS)-supported and/or –sponsored clinical trials. This policy is available on the NIAID (DAIDS) website at: <http://www.niaid.nih.gov/labsandresources/resources/daidsclinrsrch/Pages/Default.aspx>

5.3.2 Study Product Accountability

The site pharmacist is required to maintain complete records of all study products received from the NIAID CRPMC and subsequently dispensed. At US CRSs, all unused study products must be returned to the NIAID CRPMC (or as otherwise directed by the sponsor) after the study is completed or terminated. The site pharmacists at non-US CRSs must follow the instructions provided in the manual Pharmacy Guidelines and Instructions for DAIDS Clinical Trials Networks in the section Study Product Management Responsibilities for the destruction of unused study-provided products.

5.4 Study Drug Adherence Counseling

Women will be counseled during the informed consent process at the Screening Visit on the study drug regimen and the importance of maintaining the study visits. All doses will be given under DOT.

5.5 Prohibited and Precautionary Medications

Special attention should be paid to medications known to be metabolized by cytochrome P450 enzyme 3A (CYP3A) because of potential drug interactions with rifapentine, which is an inducer of metabolizing enzymes. A list of prohibited and precautionary medications may be found on the IMPAACT 2001 webpage on the IMPAACT website: <http://impaactnetwork.org/>.

5.6 Concomitant Medications

All concomitant medications will be recorded on source documents. With the exception of vitamins, topical medications, alternative therapies, and vaccines, all concomitant medications (e.g., ARVs, contraceptives) will be recorded on CRFs. Whenever a concomitant medication or study agent is initiated or a dose changed, investigators must review the concomitant medication/study agent's most recent package insert, Investigator's Brochure, or updated information from Division of AIDS, NIAID (DAIDS) to obtain the most current information on drug interactions, contraindications, and precautions.

While on the study drug regimen, currently only EFV-based and reverse transcriptase inhibitor (NRTI) based antiretroviral therapy (ART) regimens are permitted. Nevirapine (NVP), etravirine, rilpivirine, and other ART regimens (e.g., PI-based, entry inhibitors) are prohibited. Of note, infants born to mothers taking the study drug regimen can continue to receive NVP for prevention of perinatal transmission of HIV, as maternal rifapentine, like rifampin, is unlikely to affect levels of NVP in the infant (59).

6 STUDY VISITS AND PROCEDURES

An overview of the study visit and evaluations schedule is provided in Appendix I; blood draw volumes for each visit are also detailed in Appendix I. Presented in this section is additional information on visit-specific study procedures. Sections 6.7 and 6.8 below further describe Clinical Evaluations and Laboratory Evaluations, respectively. Section 10 further describes the PK specimen collection schedule.

All visits and procedures must be performed at the clinical research site or associated facilities identified in each site's approved Study Implementation Plan and must be documented in accordance with the NIAID Division of AIDS (DAIDS) policies for source documentation; refer to Section 11 for more information on documentation requirements and completion of CRFs. Refer to Section 7 for information on expedited adverse event (EAE) reporting, which may be required at any time during follow-up. As indicated in Appendix I, women will complete Screening and Entry Visits; infants will be enrolled *in utero* and will not complete Screening or Entry Visits after birth. Women will complete follow-up visits during pregnancy and postpartum; infants will complete follow-up visits postpartum.

In addition to the protocol-specified procedures listed in this section, study staff may also complete other tasks consistent with site SOPs, including but not limited to collecting, reviewing, and updating demographic and locator information; reviewing elements of informed consent; scheduling visits; providing instructions for contacting study staff between visits; providing reminders for scheduled visits; and following up on missed visits. All such tasks should be documented consistent with site SOPs. Study staff should inform women of clinically meaningful physical exam findings and laboratory test results when available.

